- 1 Bloodwork Timing: Pre-treatment blood draws may be done the day prior to treatment if necessary, and when treatment is to begin on a Monday, may be done on the previous Friday (maximum 72 hours prior to treatment). In order to ensure that nadir counts are not missed, every effort should be made to do interim blood draws within 24 hours of the day specified in the protocol.
- 2 Confirmation that the patient would meet the requirements for randomization (CBC with differential, serum creatinine, bilirubin, and AST&/or ALT only). These lab results may be ascertained based on patient chart review. It is not necessary to repeat these labs prior to the screening step for the purposes of this study, if results already available within the previous 28 days.
- 3 It is preferable that both amylase and lipase are assessed. For sites where only 1 of these parameters is routinely measured then either lipase or amylase is acceptable.
- 4 Free T3 and free T4 will be measured if TSH is abnormal.
- 5 To be done additionally every 3 months thereafter to follow abnormal lab results felt related until resolved to  $\leq$  Grade 2.
- 6 Women of child-bearing potential only (urine or serum test). Must be performed within 72 hours prior to administration of study drug. To be done every 4 weeks when on-study.
- 7 Tumor markers including CEA, CA-125, CA-19-9, etc., as indicated per standard of care testing for primary tumor. If elevated at baseline, will be monitor serially. If not elevated at baseline, will not be monitored serially.
- 8 Studies at time of progression at the discretion of patients and treating physician if feasible (optional).
- 9 To be done every 12 weeks until relapse or progression (iCPD) for up to 2 years, for patients with CR/ICR, PR/iPR, SD/iSD response as defined in Section 8.0. For patients with iUPD, confirmatory scans must be performed at least 4 weeks, but no longer than 8 weeks, after iUPD was identified.
- 10 First tumor assessment should be performed 12 weeks ( $\pm$  1 week) following randomization. To ensure comparability, baseline scans and subsequent scans to assess response must be performed using identical technique (i.e. scans performed immediately following bolus contrast administration using a standard volume of contrast, the identical contrast agent, and preferably the same scanner). Maintain schedule every 12 weeks even if cycles are delayed.

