### 7.1 Treatment Plan

#### 7.1.1 Drug Administration

When nivolumab is given with ipilimumab, nivolumab will be administered first. Prior to the ipilimumab infusion, the patient's line should be flushed and filter changed. The ipilimumab infusion should not be started until 30 minutes after the end of the nivolumab infusion.

One cycle will be defined as 6 weeks.

Arm	Agent(s)	Dose	Route	Duration	Schedule
1 & 2	Nivolumab	240 mg	IV	30 min	Day 1, then every 2 weeks
2	Ipilimumab	1 mg/kg	IV	30 min	Day 1, then every 6 weeks

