#### 7.1.4.2 *Discontinuation (Unacceptable Toxicity)*

Treatment should be permanently discontinued for the following:

- Any Grade 2 drug-related uveitis or eye pain or blurred vision that does not respond to topical therapy and does not improve to Grade 1 severity within the re-treatment period OR requires systemic treatment.
- Any Grade 3 non-skin, drug-related adverse event lasting  $>$  7 days, with the following exceptions for drug-related laboratory abnormalities, uveitis, pneumonitis, bronchospasm, diarrhea, colitis, neurologic toxicity, hypersensitivity reactions, and infusion reactions:
  - Grade 3 drug-related uveitis, pneumonitis, bronchospasm, diarrhea, colitis, neurologic toxicity, hypersensitivity reaction, or infusion reaction of any duration requires discontinuation

- Grade 3 drug-related laboratory abnormalities do not require treatment discontinuation except:
  - Grade 3 drug-related thrombocytopenia > 7 days or associated with bleeding requires discontinuation
  - Any drug-related liver function test (LFT) abnormality that meets the following criteria require discontinuation:
    - AST or ALT > 8 x ULN
    - Total bilirubin > 5 x ULN
    - Concurrent AST or ALT > 3 x ULN and total bilirubin > 2 x ULN
- Any Grade 4 drug-related adverse event or laboratory abnormality, except for the following events which do not require discontinuation:
  - Isolated Grade 4 amylase or lipase abnormalities that are not associated with symptoms or clinical manifestations of pancreatitis and decrease to < Grade 4 within 1 week of onset.
  - Isolated Grade 4 electrolyte imbalances/abnormalities that are not associated with clinical sequelae and are improved with supplementation/appropriate management within 72 hours of their onset.
- Any dosing interruption lasting > 6 weeks with the following exceptions:
  - Dosing interruptions to allow for prolonged steroid tapers to manage drug-related adverse events are allowed. Prior to re-initiating treatment in a patient with a dosing interruption lasting > 6 weeks, the CCTG must be consulted. Tumor assessments should continue as per protocol even if dosing is interrupted.
  - Dosing interruptions > 6 weeks that occur for non-drug-related reasons may be allowed if approved by CCTG. Prior to re-initiating treatment in a patient with a dosing interruption lasting > 6 weeks, CCTG must be consulted. Tumor assessments should continue as per protocol even if dosing is interrupted.

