#### 8.1.2 Evaluable for Response

All patients who have received at least one cycle of therapy and have their disease re-evaluated will be considered evaluable for response (exceptions will be those who exhibit objective disease progression prior to the end of cycle 1 who will also be considered evaluable). Patients on therapy for at least this period and who meet the other listed criteria will have their response classified according to the definitions set out below [Seymour 2017].

Response and progression will be evaluated in this study using the revised international criteria (1.1) proposed by the RECIST (Response Evaluation Criteria in Solid Tumors) committee as well as the modified iRECIST guidelines [Seymour 2017]. Investigators should note the different requirements for confirmatory scans as well as follow up for the two criteria.

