10.4 Follow-up Off Protocol Treatment

All patients will be seen at 4 weeks after completion of protocol therapy. Continued follow-up required for all patients every 3 months to collect information on ongoing toxicities, late toxicities (including second malignancies) and survival data. This follow-up will continue until death or conclusion of the trial.

PROTOCOL DATE: 2018-MAY-30

CRI-CCTG: 0001

CCTG: IND.235

For patients who go off protocol treatment with CR/ICR, PR/iPR, SD/iSD or iUPD ongoing, tumor assessments will be required every 3 months until relapse (see Section 5.0 for investigations to be performed). Please note for patients who go off protocol treatment with iUPD, confirmatory scans should be performed at least 4 weeks, but no longer 8 weeks, after iUPD was documented.

A Death report will be required on all patients. Due within 2 weeks of knowledge of death (see Appendix IV- Documentation for Study).

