### 13.2 Endpoints and Analysis

The primary endpoint is ORR by RECIST 1.1 in immunotherapy naïve patients with advanced solid tumors with detectable mutations as determined by central blood-based assay (cfDNA for POLE/D1 mutations). Patients with detectable mutations in tissue but with no detectable mutations based on plasma cfDNA will be excluded from this analysis.

Response rates will be reported using percentages over all randomized patients with 90% exact confidence intervals (CI) of each arm in a non-comparative analysis. In addition, exact logistic regression models will be used to assess the effect of treatment on objective response probability, adjusting for mutational load values and trial site.

Secondary endpoints include: ORR of nivolumab monotherapy and of nivolumab combined with ipilimumab in all treated patients. Response rates will be reported using percentages over all patients who have received at least one dose of treatment with 90% exact CI of each arm in a non-comparative analysis. In addition, exact logistic regression models will be used to assess the effect of treatment on objective response probability, adjusting for mutational load values and trial site.

Duration of response (DOR) will be calculated from time of response to documentation of progression or death or censored at last time of disease assessment among all patients who have responded. Kaplan-Meier method will be used to estimate median duration of response and 90% confidence interval in each arm.

The responses assessed by iRECIST will be analyzed similarly as that by RECIST 1.1.

To assess the safety and characterize toxicities of nivolumab combined with ipilimumab and nivolumab monotherapy in all patients, estimation of the adverse event profile associated with treatment will be performed. All toxicities regardless of attribution will be reported using the CTCAE version 5.0 criteria. Adverse events rates will be reported using percentages with 90% exact CI.

Correlation between detectable mutations in tumor and detectable mutations in blood will be assessed by Fischer's exact test in each arm.

Detectable mutations in the initial study population are *POLE*/*POLD1* mutations based on plasma cfDNA.

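### Sections 8.1.2 and 8.2.5 together leave a patient who stops in cycle 1 without progression and responds at week 12 with no route to count as a responder, though 13.2 keeps that patient in the ORR denominator

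*Combined protocol and SAP*

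**What the plan says.** All references are to the combined protocol and SAP.

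- **Evaluability (8.1.2).** "All patients who have received at least one cycle of therapy and have their disease re-evaluated will be considered evaluable for response". The one carve-out reads "exceptions will be those who exhibit objective disease progression prior to the end of cycle 1 who will also be considered evaluable". The next sentence makes the condition operative: "Patients on therapy for at least this period and who meet the other listed criteria will have their response classified".
- **Cycle length (7.1.1).** "One cycle will be defined as 6 weeks".
- **First scan (5.0, footnote 10).** "First tumor assessment should be performed 12 weeks", plus or minus 1 week, counted from randomization.
- **Best-response window (8.2.5, and Table 3 for iRECIST).** Best response is to be classified for all patients, but only between the start and the end of study treatment.
- **Early stopping (7.1.4.2).** "Grade 3 drug-related uveitis, pneumonitis, bronchospasm, diarrhea, colitis, neurologic toxicity, hypersensitivity reaction, or infusion reaction of any duration requires discontinuation". A permanent stop in cycle 1 is therefore foreseeable.
- **Denominators (13.2).** Primary ORR: "Response rates will be reported using percentages over all randomized patients", leaving out patients without a cfDNA-detectable mutation. Secondary ORR: everyone with at least one dose. No rule says how a patient who is not evaluable under 8.1.2 is scored.
- **Off-treatment scans (10.4; footnote 9 is similar).** "For patients who go off protocol treatment with CR/ICR, PR/iPR, SD/iSD or iUPD ongoing, tumor assessments will be required every 3 months until relapse".

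**The concern.** Take a patient who has a listed grade 3 event on day 20, stops all protocol treatment, and shows a 40% decrease in target lesions at week 12. This patient has not had a full cycle, so 8.1.2 does not classify the response. Treatment ended before the scan, so 8.2.5 does not capture it either. Had the same patient progressed before week 6, 8.1.2 would have classified the outcome. The asymmetry runs one way: early failures are counted and early-stopping responders are not.

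Two outcomes are possible, and the plan does not choose between them.

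1. If 13.2 sets the denominator and 8.1.2 with 8.2.5 sets the numerator, a true responder counts as a failure and ORR is understated.
2. If analysts follow the evaluable-patient wording in 13.1 and 13.3, the patient is dropped. Membership of the analysis set then depends on a post-randomization event, and ORR is no longer over all randomized patients.

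The trial is open-label and 11.1 provides no central radiology review, so this choice should be fixed before the data are seen.

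**Working it through.** **Inputs.** From 13.3: 50 evaluable patients per arm; null and target ORR of 13% and 30% (nivolumab) and 30% and 50% (combination); two-sided alpha 0.10, so 0.05 per tail; 90% power. From 13.2: exact 90% confidence intervals. The plan states no success rule. I assume success means that the exact 90% lower limit exceeds the null rate.

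**Step 1: the plan's own power.** Find the smallest r with P(X ≥ r | 50, p0) ≤ 0.05; power is P(X ≥ r | 50, p1).

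- Combination: r = 21, since P(X ≥ 21 | 0.30) = 0.048 and P(X ≥ 20 | 0.30) = 0.085. Power is P(X ≥ 21 | 0.50) = 89.9%, which reproduces the stated 90%.
- Nivolumab: r = 12 (tail 0.024) gives 86.1%. With r = 11 power is 92.1%, but the tail is 0.0535. The one-sample normal approximation needs n = 46, so the stated 90% is reasonable on that basis.

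**Step 2: the timeline.** Cycle 1 ends at week 6 and the first scheduled scan is at week 12 (weeks 11 to 13). A patient who stops in cycle 1 has no scheduled on-treatment scan. A response first seen at week 12 fails two separate conditions: one cycle of therapy (8.1.2) and a date before the end of treatment (8.2.5, Table 3). Removing either one alone leaves the other in force.

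**Step 3: size if the patient stays in the denominator.** Let k of 50 patients stop in cycle 1 without progression, and assume they would have responded at the arm's target rate. The observable ORR is p1 × (1 − k/50). The documents do not give k; I use 1 to 3.

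| k | Combination ORR | Power (≥ 21/50) | Nivolumab ORR | Power (≥ 12/50) |
|---|---|---|---|---|
| 0 | 50.0% | 89.9% | 30.0% | 86.1% |
| 1 | 0.50 × 0.98 = 49.0% | 87.1% | 0.30 × 0.98 = 29.4% | 84.0% |
| 2 | 0.50 × 0.96 = 48.0% | 83.9% | 0.30 × 0.96 = 28.8% | 81.6% |
| 3 | 0.50 × 0.94 = 47.0% | 80.2% | 0.30 × 0.94 = 28.2% | 79.1% |

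Expected responders lost in the combination arm are 0.5 × k, that is 0.5 to 1.5.

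**Step 4: size if the patient is dropped instead.** With two combination patients dropped, n = 48, the threshold is still 21 (tail 0.030), and power at 50% is 84.4%.

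**Step 5: what one patient can do at the boundary.** The exact 90% lower limit is 30.1% at 21/50 and 28.3% at 20/50, against a null of 30%. For nivolumab it is 14.5% at 12/50 and 12.9% at 11/50, against 13%. One unclassified responder can reverse the conclusion in either arm.

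**The case against.** **The text is less settled than a fixed bar.** Section 8.1.2 says who is evaluable and never labels the others non-responders; 8.2.5 speaks of all patients; 13.2 does not refer to 8.1.2. This is fair, and it is why the outcome splits into the two cases above. It does not rescue the patient. In one case the response is a failure, in the other the patient is absent, and the all-patients wording of 8.2.5 stops at the end of treatment.

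**A reader might infer that 8.1.2 alone causes the loss and that editing it would suffice.** The documents do not support this. The 8.2.5 window already excludes the same week-12 response, so the figures above are a joint effect. If the window is raised as a separate point, the loss must not be counted twice.

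**A reader might infer that the combination arm is hit harder.** Section 2.6 reports grade 3/4 events of 33% (every-6-week ipilimumab cohort) against 19% (monotherapy), which makes it plausible. But the mechanism is stopping treatment, and the same section describes discontinuations for treatment-related grade 3-4 events as similar to monotherapy. Section 7.1.4.2 also has discontinuation assessed separately for each drug, so some combination patients may stay on nivolumab and complete the cycle.

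**A reader might take the 8% discontinuation rate in 2.6 as the size.** It comes from another trial and covers any time on treatment, not cycle 1.

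**A reader might infer that sites are told to stop scanning these patients.** They are not. Sections 10.4 and footnote 9 omit a patient who has never been scanned on study, but footnote 10 times the first scan from randomization, 8.2 requires assessments until unequivocal progression, and 10.1 asks sites to keep the schedule after a premature stop. Only clarification is needed.

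**The bias is conservative if these patients count as failures.** That is true, but an avoidable understatement of the primary endpoint is still a cost in arms with 50 patients each.

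**Conclusion.** The point holds as a joint defect of 8.1.2 and the treatment-bound window in 8.2.5 and Table 3, set against the denominators in 13.2. A patient who stops in cycle 1 without progression and responds at week 12 cannot reach the numerator under the text as written.

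The likely size is modest and rests on assumptions: the cycle-1 stopping count, response in those patients at the target rate, and the success rule. With 1 to 3 of 50 combination patients affected, power falls from 89.9% to between 87.1% and 80.2%. A difference between the arms is possible but not established. The correction should be made: it is cheap, and one patient can decide the result at the boundary.

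**What to change.** - **8.1.2:** drop the one-cycle condition for ORR.
- **8.2.5 and Table 3:** replace the end-of-treatment cut-off. Classify response for every patient in the 13.2 populations from any post-baseline assessment up to progression or the start of new anti-cancer therapy, whatever the amount of treatment received.
- **13.2:** state that patients with no post-baseline assessment count as non-responders.
- **10.4 and footnote 9:** make clear that patients who stop before their first scan stay on the 12-week schedule.
- **Sensitivity analysis:** keep the 8.1.2 evaluable set only for an analysis labelled as such.

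The 8.1.2 and window edits must go together, because either alone leaves the response uncounted. The cost is protocol wording and a few off-treatment scans; the week-12 scan is already timed from randomization. Nothing here changes dosing or the discontinuation rules.

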### 8.2 Response and Evaluation Endpoints

Response and progression will be evaluated in this study using the revised international criteria (1.1) proposed by the RECIST (Response Evaluation Criteria in Solid Tumors) committee as well as the Immune-Related modified RECIST. Investigators should continue treatment, as appropriate, in the absence of unacceptable toxicity, until unequivocal disease progression. This is particularly important for patients in whom pseudoprogression may have occurred. Follow up response assessments must be continued until unequivocal disease progression has occurred.

#### 8.2.1 Measurable Disease

Measurable tumor lesions (nodal, subcutaneous, lung parenchyma, solid organ metastases) are defined as those that can be accurately measured in at least one dimension (longest diameter to be recorded) as  $\geq 20$  mm with chest x-ray and as  $\geq 10$  mm with CT scan or clinical examination. Bone lesions are considered measurable only if assessed by CT scan and have an identifiable soft tissue component that meets these requirements (soft tissue component  $\geq 10$  mm by CT scan). *Malignant lymph nodes* must be  $\geq 15$  mm in the short axis to be considered measurable; only the short axis will be measured and followed. All tumor measurements must be recorded in millimeters (or decimal fractions of centimeters). Previously irradiated lesions are not considered measurable unless progression has been documented in the lesion.

#### 8.2.2 Non-measurable Disease

All other lesions (or sites of disease), including small lesions are considered non-measurable disease. Bone lesions without a measurable soft tissue component, leptomeningeal disease, ascites, pleural/pericardial effusions, lymphangitis cutis/pulmonis, inflammatory breast disease, lymphangitic involvement of lung or skin and abdominal masses followed by clinical examination are all non-measurable. Lesions in previously irradiated areas are non-measurable, unless progression has been demonstrated.

8.2.3 Target Lesions

When more than one measurable tumor lesion is present at baseline all lesions up to *a maximum of 5 lesions total* (and a maximum of *2 lesions per organ*) representative of all involved organs should be identified as target lesions and will be recorded and measured at baseline. Target lesions should be selected on the basis of their size (lesions with the longest diameter), be representative of all involved organs, but in addition should be those that lend themselves to *reproducible repeated measurements*. Note that pathological nodes must meet the criterion of a short axis of  $\geq 15$  mm by CT scan and only the *short axis* of these nodes will contribute to the baseline sum. All other pathological nodes (those with short axis  $\geq 10$  mm but  $< 15$  mm) should be considered non-target lesions. Nodes that have a short axis  $< 10$  mm are considered non-pathological and should not be recorded or followed (see 8.2.4). At baseline, the sum of the target lesions (longest diameter of tumor lesions plus short axis of lymph nodes: overall maximum of 5) is to be recorded.

After baseline, a value should be provided on the CRF for all identified target lesions for each assessment, even if very small. If extremely small and faint lesions cannot be accurately measured but are deemed to be present, a default value of 5 mm may be used. If lesions are too small to measure and indeed are believed to be absent, a default value of 0 mm may be used.

8.2.4 Non-target Lesions

All non-measurable lesions (or sites of disease) plus any measurable lesions over and above those listed as target lesions are considered *non-target lesions*. Measurements are not required but these lesions should be noted at baseline and should be followed as “present” or “absent”.

8.2.5 Response

All patients will have their BEST RESPONSE from the start of study treatment until the end of treatment classified as outlined below:

**Complete Response (CR):** disappearance of *target* and *non-target* lesions and normalization of tumor markers. Pathological lymph nodes must have short axis measures  $< 10$  mm (Note: continue to record the measurement even if  $< 10$  mm and considered CR). Residual lesions (other than nodes  $< 10$  mm) thought to be non-malignant should be further investigated (by cytology specialized imaging or other techniques as appropriate for individual cases [Seymour 2017]) before CR can be accepted. Confirmation of response is only required in non-randomized studies.

**Partial Response (PR):** at least a 30% decrease in the sum of measures (longest diameter for tumor lesions and short axis measure for nodes) of target lesions, taking as reference the baseline sum of diameters. Non target lesions must be non-PD. Confirmation of response is only required in non-randomized studies.

**Stable Disease (SD):** Neither sufficient shrinkage to qualify for PR nor sufficient increase to qualify for PD taking as reference the smallest sum of diameters on study.

Progressive Disease (PD): at least a 20% increase in the sum of diameters of measured lesions taking as references the smallest sum of diameters recorded on study (including baseline) AND an absolute increase of  $\geq 5$  mm. Appearance of new lesions will also constitute progressive disease (including lesions in previously unassessed areas). In exceptional circumstances, unequivocal progression of non-target disease may be accepted as evidence of disease progression, where the overall tumor burden has increased sufficiently to merit discontinuation of treatment or where the tumor burden appears to have increased by at least 73% in volume. Modest increases in the size of one or more non-target lesions are NOT considered unequivocal progression. If the evidence of PD is equivocal (target or non-target), treatment may continue until the next assessment, but if confirmed, the earlier date must be used.

Patients that are clinically well may continue on therapy following RECIST progression with new lesions or increase in target lesions if the increase in disease burden does not meet the definition of PD by immune response criteria [Seymour 2017]. In this situation, patients do not have unequivocal progression until immune response criteria are met (see Table 1 below).

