Non-iUPD/PD	Non-iUPD/PD	Yes	iUPD	Remains iUPD unless iCPD confirmed based on - increase in size or number of new lesions previously identified

\* Using RECIST 1.1 principles. If no PSPD occurs, RECIST 1.1 and iRECIST categories for CR, PR and SD would be the same.

\*\* In any lesion category.

\*\*\* Previously identified in assessment immediately prior to this TP.

Table 3: iRECIST Best Overall Response (iBOR)

All patients will have their iBOR from the start of study treatment until the end of treatment classified as outlined below.

TPR1	TPR2	TPR3	TPR4	TPR5	iBOR
iCR	iCR, iPR, iUPD, NE	iCR, iPR, iUPD, NE	iUPD	iCPD	iCR
iUPD	iPR, iSD, NE	iCR	iCR, iPR, iSD, iUPD, NE	iCR, iPR, iSD, iUPD, iCPD, NE	iCR
iUPD	iPR	iPR, iSD, iUPD, NE	iPR, iSD, iUPD, NE, iCPD	iPR, iSD, iUPD, NE, iCPD	iPR
iUPD	iSD, NE	PR	iPR, iSD, iUPD, NE	iPR, iSD, iUPD, iCPD, NE	iPR
iUPD	iSD	iSD, iUPD, NE	iSD, iUPD, iCPD, NE	iSD, iUPD, ICPD, NE	iSD
iUPD	iCPD	Anything	Anything	Anything	iCPD
iUPD	iUPD	iCPD	Anything	Anything	iCPD
iUPD	NE	NE	NE	NE	iUPD

 
• Table assumes a randomized study where confirmation of CR or PR is not required.
 
• NE = not evaluable that cycle.
 
• Designation “T” for BOR can be used to indicate prior iUPD to aid in data interpretation.
 
• For patients with non-target disease only at baseline, only CR or non-CR/non-PD can be assigned at each TPR but is not shown in the table for ease of presentation.
 
					

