#### 8.4 Response Duration (RECIST 1.1 and iRECIST)

Response duration will be measured from the time measurement criteria for CR/PR (whichever is first recorded) are first met until the first date that recurrent or progressive disease is objectively documented, taking as reference the smallest measurements recorded on study (including baseline).

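### Best response and iBOR close at an undefined end of treatment, so read literally a pre-progression CR or PR first seen on a later off-treatment protocol scan is not counted in ORR

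*Combined protocol and SAP*

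**What the plan says.** Section 8.2.5 is the only place that classifies RECIST 1.1 best response, and it fixes the period: "All patients will have their BEST RESPONSE from the start of study treatment until the end of treatment classified as outlined below". Table 3 in section 8.3 does the same for the immune criteria: "All patients will have their iBOR from the start of study treatment until the end of treatment classified as outlined below". Neither section says whether the end of treatment is the last dose, the decision to stop or the 4-week post-treatment visit.

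Section 13.2 makes ORR by RECIST 1.1 the primary endpoint. It reports ORR over all randomized patients (leaving out those with no mutation in plasma) with exact 90% intervals per arm, and gives no response window of its own.

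Other sections carry assessment beyond treatment:

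- Section 8.2: "Follow up response assessments must be continued until unequivocal disease progression has occurred".
- Section 5.0, footnote 9, which is attached to the post-treatment imaging columns: "To be done every 12 weeks until relapse or progression (iCPD) for up to 2 years, for patients with CR/ICR, PR/iPR, SD/iSD response".
- Section 10.4 requires 3-monthly tumour assessments for patients who leave treatment with CR, PR, SD or iUPD ongoing.
- Section 10.1 asks sites to try to keep the investigation schedule after early stopping.
- Section 8.4 measures response duration from when the CR or PR criteria "are first met until the first date that recurrent or progressive disease is objectively documented", with no end-of-treatment limit.

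**The concern.** The plan collects scans in patients who have stopped treatment without progressing, then defines best response so that those scans cannot contribute to it. Take a patient who stops for toxicity with stable disease and meets PR at the next protocol scan, with no progression and no new therapy in between. That patient stays in the denominator of the primary endpoint but, on the literal wording, cannot enter the numerator. The iRECIST endpoint does not recover the response, because iBOR closes at the same point.

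The same patient's place in the duration-of-response analysis is unclear. Section 8.4 would let the response start off treatment, while section 13.2 restricts the analysis to patients who have responded.

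Because the end of treatment is undefined, two analysts could also score a scan taken shortly after the last dose differently.

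**Working it through.** **Which text governs.** Section 13.2 does not cite 8.2.5. However, 8.2.5 holds the only RECIST 1.1 response classification, and section 8.1.2 sends evaluable patients to the definitions that follow it. No section extends the window. If 8.2.5 did not govern, the primary endpoint would have no window at all.

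**The plan's own figure.** Section 13.3 gives 50 evaluable patients per arm, 90% power and two-sided alpha 0.10. It sets p0 = 13% and p1 = 30% for nivolumab, and p0 = 30% and p1 = 50% for the combination. I take success to mean that the exact 90% interval lies above p0. This is inferred from sections 13.2 and 13.3, not stated. The cut-off is the smallest count whose Clopper-Pearson lower limit exceeds p0:

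- Nivolumab: 12/50 (lower limit 0.1447; 11/50 gives 0.1286). P(X ≥ 12 | 0.13) = 0.0242; power P(X ≥ 12 | 0.30) = 0.8610.
- Combination: 21/50 (lower limit 0.3014; 20/50 gives 0.2831). P(X ≥ 21 | 0.30) = 0.0478; power P(X ≥ 21 | 0.50) = 0.8987.

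The combination arm reproduces 90%. The nivolumab arm reaches it by normal approximation (0.922) but not by the exact rule. That gap comes from binomial discreteness and is a separate matter.

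**Size of the loss.** The documents give no rate of first response after stopping, so these inputs are assumptions:

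- Share stopping early, s = 5% to 8%. This borrows from section 2.6, where treatment-related grade 3-4 events led to discontinuation in 5% and 8% of two combination cohorts of an NSCLC trial. The population differs and the figure is not all-cause.
- Share of those patients' responses that first appear after stopping, f = 10% to 30%.
- Patients who stop early respond at rate p1, and p1 counts off-treatment responses.

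Loss in ORR = s × f × p1, and power is recomputed at p1 minus the loss.

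| Arm | Loss in ORR | ORR measured | Exact power |
|---|---|---|---|
| Nivolumab, low | 0.05 × 0.10 × 0.30 = 0.0015 | 0.2985 | 0.856 |
| Nivolumab, high | 0.08 × 0.30 × 0.30 = 0.0072 | 0.2928 | 0.835 |
| Combination, low | 0.05 × 0.10 × 0.50 = 0.0025 | 0.4975 | 0.892 |
| Combination, high | 0.08 × 0.30 × 0.50 = 0.0120 | 0.4880 | 0.865 |

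In patients, 50 × 0.05 = 2.5 to 50 × 0.08 = 4 per arm stop early. The expected number of uncounted responses is 50 × 0.0015 = 0.075 to 50 × 0.0072 = 0.36 for nivolumab, and 50 × 0.0025 = 0.125 to 50 × 0.012 = 0.6 for the combination.

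**The case against.** The case for leaving the text alone has substance. Treatment runs to progression with no maximum duration and may continue beyond it (sections 7.2 and 10.2), so few patients stop while a first response is still possible. An on-treatment window keeps out responses due to later therapy, which section 10.3 leaves to the investigator. The documents do not say what window p1 assumes; if p1 is an on-treatment rate, power against it does not fall. All of this limits the size. It does not remove the conflict between the window and the scans, and censoring at new therapy deals with contamination more directly.

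A reader might also infer more than the documents support:

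- *That power drops to 73-76% for nivolumab.* The 76.3% figure needs a loss of 0.08 × 0.30 = 2.4 points, meaning 30% of all early stoppers respond late. At p1 = 30% that is every response in that group. The 73.3% figure needs a 3-point loss, or 0.03/0.08 = 37.5% of stoppers, which exceeds p1. Neither is an expected effect.
- *That a patient stopping between weeks 6 and 12 is the clearest case.* Section 8.1.2 says "All patients who have received at least one cycle of therapy and have their disease re-evaluated will be considered evaluable for response", a cycle is 6 weeks, and in footnote 10 of section 5.0 "First tumor assessment should be performed 12 weeks" after randomization. But the off-treatment scans required by section 10.4 and footnote 9 apply to patients with a recorded response status, which this patient lacks. Only the general wording of section 8.2 and the best-efforts wording of section 10.1 cover the scan.
- *That section 7.1.4.2 is further evidence.* Its sentence "Tumor assessments should continue as per protocol even if dosing is interrupted" concerns patients whose dosing is interrupted. They are still on treatment, so the window remains open.
- *That late responders are excluded from duration of response.* Sections 8.4 and 13.2 point in different directions, so this is unclear rather than settled.

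**Conclusion.** The point holds as a conflict between the stated response window and the plan's own assessment schedule. On the literal wording, a CR or PR first seen off treatment, before progression and before new therapy, is not counted under RECIST 1.1 or iRECIST. This rests on reading 8.2.5 as the definition behind the primary ORR, which is the natural reading but is not spelled out in 13.2.

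The effect on ORR can only be downward, and could differ between arms if early stopping does. It is probably small: under the assumptions above, less than one expected response per arm, about 0.15-0.7 points of ORR for nivolumab and 0.25-1.2 for the combination. The corresponding losses of exact power are about 0.5-2.6 and 0.6-3.4 percentage points. The case for change is that the wording defines the primary numerator and is cheap to put right, not that the trial's power is in danger.

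**What to change.** In sections 8.2.5 and 13.2, define RECIST 1.1 best response as the best response up to first RECIST 1.1 PD or the start of non-protocol anticancer therapy, whichever is earlier, whether or not protocol treatment has stopped. Add a sentence that responses after RECIST 1.1 PD count only under iRECIST; section 8.3 implies this but 8.2.5 does not say it. In section 8.3, run iBOR to iCPD or the start of non-protocol anticancer therapy, whichever is earlier. Say in 13.2 that responders under this definition enter the duration-of-response analysis. Keep the rule that CR and PR need no confirmation. Moving the start of the window to randomization is optional, since treatment begins within 2 working days of it.

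Sample size, treatment and the scan schedule do not change. The cost is data capture: section 7.3 records medication at entry and during protocol therapy, and the form list in Appendix IV does not name subsequent anticancer therapy. Its start date would have to be added to the end-of-treatment or follow-up report, with minor extra analysis work.
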